3.5.1 Lost to Follow up Procedure

- When a participant is lost to follow-up, the last data collected will be entered in the database for each missed subsequent visit.

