3.5 Withdrawal Procedure, Dropouts

- Participants with uneven sacroiliac joints who do not experience any relief after doing the correction exercises and/or trying out the pelvic support belt will probably not want to continue to try these exercises or wear the pelvic support belt at home.
- They will, however, be asked to try the exercise and belt at home and return in 1 month to be retested and fill out the questionnaires. At that time, all the procedures associated with the first treatment visit will be repeated.
- For those who decide to withdraw from the study, every effort will be made to contact them and ask them the questionnaire relevant to the time they withdrew,
- unless, at the time they withdraw they notify us that they do not want to answer any more questionnaires, in which case the last data collected will be entered in the database.

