5.0 Statistics

5.1 Outcome Measures

5.1.1A Primary Outcomes For the First Study

- difference in the change in ODI score in the initial treatment visit questionnaire and at the assessment visit one month later in the control group compared to the change from the treatment visit questionnaire to the 1 month assessment follow-up visit in the immediate SIFFT and exercise treatment group.
- difference in the change in ODI score in the treatment visit questionnaire and at the assessment visit, one month later, in the control group compared to the change from the treatment visit questionnaire to the 1 month assessment follow-up visit in the immediate pelvic support belt treatment group.

5.1.2A Secondary Outcomes For the First Study

- difference in the change in BPI NRS pain severity scores in the treatment visit questionnaire and at the assessment visit, one month later, in the control group compared to the change from the treatment visit questionnaire to the 1 month follow-up assessment visit in the immediate SIFFT and exercise treatment group.
- difference in the change in BPI NRS pain severity scores in the treatment visit questionnaire and at the assessment visit, one month later, in the control group compared to the change from the treatment visit questionnaire to the 1 month follow-up assessment visit in the immediate pelvic support belt treatment group.

5.1.1B Primary Outcome For the Follow-up Study

- difference in the change in ODI score in the assessment visit questionnaire and at the reassessment visit, two months later, for all groups.

5.1.2B Secondary Outcome For the Follow-up Study

- difference in the change in BPI NRS pain severity scores in the assessment visit questionnaire and at the reassessment visit, two months later, for all groups.

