5.2 Statistical Analysis

Data will be analyzed using PASW Statistics 18, Release 18.0.0, IBM. Analysis will be performed by intention-to-treat. Descriptive statistics (mean value \pm standard deviation (SD)) will be calculated for outcome variables at each time point. Baseline between-group data will be analyzed for significant differences by t-tests for nominal variables and Pearson chi square tests for categorical variables. Baseline characteristics will be included in the model as covariates for those variables with a significant between group difference. Analyses of covariates will be applied to compare the groups for magnitude of change in the 0-10 NRS pain score and Oswestry Disability Index between baseline and each follow-up time point (0, 1 and 2 months). A two-tailed P value $<.05$ will be used as the statistical significance level.

- a Pearson's chi-square-test will be done to assess the significance of the difference in Oswestry low back disability score over a 1 month period between

those who are treated with the immediate SIFFT and exercise treatment group, the immediate pelvic support belt group and those who are in the observation group.

- A second Pearson's chi-square will be done to assess the significance of the difference in BPI NRS pain severity score over a 1 month period between those who are treated with the immediate SIFFT and exercise treatment group, the immediate pelvic support belt group and those who are in the observation group.
- A student t-test will be done to assess the significance of the difference in ODI score over a one month period when both treatments are used simultaneously.
- A student t-test will be done to assess the significance of the difference in BPI NRS pain severity score over a one month period when both treatments are used simultaneously.
- The average and standard deviation for all the other data will be calculated and reported on.

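### Sections 3.5 and 3.5.1 copy the last score forward in the database, so a missed ODI interval is analysed as an observed change of zero, and section 5.2 provides no check on that assumption

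*Combined protocol and SAP*

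**What the plan says.** - **Lost to follow-up (section 3.5.1).** "the last data collected will be entered in the database for each missed subsequent visit". The rule acts on the database, not only on an analysis file.
- **Withdrawal (section 3.5).** For people who withdraw, "every effort will be made to contact them and ask them the questionnaire relevant to the time they withdrew". The exception is those who say they "do not want to answer any more questionnaires, in which case the last data collected will be entered in the database". This text names no visits, and it does not say which visit a withdrawal questionnaire counts for.
- **Reason for stopping (section 3.5).** Participants "who do not experience any relief after doing the correction exercises and/or trying out the pelvic support belt will probably not want to continue" with the treatment at home, but they are asked to try it and to return at one month.
- **Outcomes (section 5.1).** All ODI and BPI outcomes are changes between visits: treatment visit to month 1 in the first study, and for the follow-up study the "difference in the change in ODI score in the assessment visit questionnaire and at the reassessment visit".
- **Analysis (section 5.2).** "Analysis will be performed by intention-to-treat". Groups are also compared on change "between baseline and each follow-up time point (0, 1 and 2 months"). No missing-data method, assumption or sensitivity analysis is given there or elsewhere.

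**The concern.** A copied score subtracted from itself is zero. Once it is in the database, that zero looks like a measured result, and the data lists in section 4 include no flag to separate copied scores from real ones. The copied zero is right only if the people lost did not change. Otherwise the estimate shifts, unless the errors happen to cancel.

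Unequal loss is plausible because groups 1 and 2 are treated at once while group 3 waits a month. The waiting list continues its usual treatments (section 1.1), so it may improve too. Stating intention-to-treat does not settle the matter: it says who is analysed, not what value stands in for a missing score. This is a pilot, but section 5.2 still plans formal tests at P < .05 on these changes, and its estimates may be used to plan a larger trial.

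**Working it through.** **Inputs from the documents.** 20 per group, and 3 × 20 = 60 as section 2.2 states. Two-sided 5% level (section 5.2). No power, SD, mean change or loss rate is stated, so there is no planned figure to reproduce.

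**Assumptions.** The 10% margin in section 1.2 is taken as 10 ODI points. SD of change is 12 or 18, and loss is 10% to 30%. Improvement counts as positive.

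**Step 1: what the rule does to each person.** Let Y0, Y1 and Y2 be the scores at baseline, month 1 and month 2.
- Lost before month 1: Y1 and Y2 are both set to Y0, so the change is 0 in both sub-studies.
- Lost after month 1: Y2 is set to Y1, so the month 1 to 2 change is 0, but the baseline-to-month-2 change keeps the observed Y1 − Y0.
- Example: improvement of 10 by month 1 and 5 more by month 2, with 10% lost before and 10% after month 1. Baseline to month 1 gives 0.9 × 10 = 9 (true 10). Month 1 to 2 gives 0.8 × 5 = 4 (true 5). Baseline to month 2 gives 0.8 × 15 + 0.1 × 10 = 13 (true 15).

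**Step 2: which score is carried.** ODI has one score per visit, so the zero is clear. For pain, section 4.2.2 also records a post-exercise rating in group 1. Section 3.5.1 does not say whether that could count as the last data, so the carried pain change need not be zero.

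**Step 3: group difference when loss is unrelated to outcome.** Expected difference = mT(1 − pT) − mC(1 − pC), where m is mean improvement and p the share lost (T treated, C control).
- 10 v 0, equal loss of 10/20/30%: 10 × 0.9 = 9; 10 × 0.8 = 8; 10 × 0.7 = 7.
- 5 v 5, loss 10% treated and 30% control: 5 × 0.9 − 5 × 0.7 = +1, where the truth is 0.
- 15 v 5, loss 30%/10%: 15 × 0.7 − 5 × 0.9 = 6. With loss 10%/30%: 15 × 0.9 − 5 × 0.7 = 10. The truth is 10 in both, so in the second case the errors cancel.
- Follow-up study, true change 5, loss 10/20/30%: 4.5, 4.0, 3.5.

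**Step 4: intervals and tests.** Simulated two-sample t analyses, 20 per arm, random loss, at least 100,000 trials per case.

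| Case | SD 12 | SD 18 |
|---|---|---|
| Coverage of 10 at 10/20/30% equal loss | about 94/91/84% | about 95/93/90% |
| Coverage of the shifted value 9/8/7 | about 95% | about 95% |
| Type I error, both improve 5, loss 10%/30% | about 6.0 to 6.2% | about 5.5 to 5.6% |
| Type I error, both improve 5, loss 20%/20% | about 5% | about 5% |

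At SD 12 the mean standard errors are 3.64/3.48/3.31, against true sampling SDs of 3.66/3.51/3.33. The lost coverage therefore comes from the shift in the estimate, not from a wrong standard error.

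**Step 5: if only people without relief are lost.** Let two thirds of the treated improve 15 and one third 0, so the true difference from unchanged controls is (2/3) × 15 = 10. Carry-forward stays at 10. Observed scores give 10/(1 − p) = 11.1, 12.5 or 14.3 at 10/20/30% treated loss. Baseline-adjusted ANCOVA gives the same values when baseline does not predict relief.
- Mixed case, 20% lost, half at random and half for no relief: carry-forward (2/3) × 0.9 × 15 = 9; observed 9/0.8 = 11.25. The truth lies between.
- If the no-relief third worsen by 5 and the rest improve 17.5 (true 10), 20% loss gives carry-forward 0.2 × 5 + 10 = 11.0 and observed 11/0.8 = 13.75.

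**The case against.** The strongest reply is that an observed-score analysis is not clearly better. Under the one pattern that section 3.5 hints at, Step 5 shows carry-forward correct or closer, and observed scores too favourable. A person with only a baseline score also adds almost nothing to the month-1 contrast in a repeated-measures model, so for the first study it is close to a comparison of completers. Both points stand. They argue for requiring two analyses, not for leaving either one alone.

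Second, section 5.2 lists chi-square tests for the one-month comparisons, and section 1.1 speaks of a clinically relevant change. If outcomes were classed as response or no response, counting a person lost as a non-responder would be a recognised convention. That is fair for that reading. But section 5.2 also plans a covariate-adjusted comparison of the size of change, and the figures above apply to it.

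Third, loss may be low: section 2.3 requires ability to attend all visits, the intervals are one month, and withdrawals are contacted. This limits the size but does not supply a check.

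A reader might also infer more than the documents support:
- That the whole result rests on carry-forward. Only the contribution of those lost does, and a withdrawal questionnaire can replace the copied zero with an observed score.
- That carry-forward is always conservative, or always harmful. Steps 3 and 5 show that the direction depends on who is lost.
- That section 3.5 predicts loss of people without relief. It expects them to want to stop treatment, not to miss visits, and it does not concern the waiting list.

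**Conclusion.** The concern holds in this form: each missed ODI interval is analysed as an observed zero, the rule for pain is ambiguous, and nothing in section 5.2 tests the assumption. Bias is toward no change under equal random loss and can go either way if loss differs by arm. In the illustrations a true 10-point difference falls to between 9 and 7, and unequal loss creates a spurious 1 point. The distortion of coverage and type I error is larger at SD 12 than at SD 18, and small near 10% loss.

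The tempting stronger conclusion, that type I error is generally inflated, is not supported: with equal random loss it stays near 5%. All sizes rest on assumed loss rates, SDs and mean changes. The textual finding does not. It should be corrected before data entry, because copied scores may be hard to identify afterwards.

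**What to change.** **Sections 3.5 and 3.5.1.** Store a missed visit as missing and copy no score forward in the database. Keep the effort to contact people who withdraw, and state which visit a withdrawal questionnaire counts for.

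**Section 5.2.**
- Analyse observed ODI and BPI scores with baseline adjustment: ANCOVA at month 1, or a repeated-measures model across visits, whose month 1 to 2 contrast serves the follow-up study. State the missing-at-random assumption.
- Name the baseline score as a covariate in every case. The present rule, "Baseline characteristics will be included in the model as covariates for those variables with a significant between group difference", does not guarantee it.
- Require a zero-change analysis for those lost, derived only in the analysis file, with the pain score that it uses defined. Report it beside the observed-score analysis, and draw a conclusion only as firm as the two together support.
- Run any listed test that is kept on data without copied scores.
- Report loss by arm and visit.

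**Cost.** Text edits, slightly more analysis work and somewhat wider intervals. The observed-score analysis can still be biased if loss depends on unobserved scores, which is why the zero-change analysis must be required and not optional.

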4.0 Data to be Collected

4.1 Data Collected on All Participants

- Date of assessment visit
- Number of participants presenting with back pain
- Month and year of birth of participants
- Sex of participants
- Duration of back pain
- Concomitant pain medications
- Cannabis and alcohol intake in the past 24 hours
- BPI NRS pain severity score (appendix 1)
- ODI questionnaire (appendix 2).
- presence of lumbar pain or hip pain
- Beighton hypermobility score
- Piriformis, gluteus medius or minimus biceps femoris and quadratus lumborum tenderness
- Size of leg length discrepancy, if present

4.2 Data Collected on All Participants with Nonaligned PSISs

4.2.1 At all visits

- Date of questionnaire (randomization and first treatment visit, one month assessment visit and two month reassessment visit)
 - Use of medications, cannabis, alcohol.
 - Use of other treatments: acupuncture, yoga, core exercises, chiropractic manipulation, massage, physiotherapy and other treatments.
 - The (ODI) questionnaire (appendix 2)
 - the BPI NRS Pain Severity Scale (appendix 1): On a scale of 0 (no pain) to 10 (worst imaginable pain) pain in the last 24 hours compared to previous recorded pain level (the participant will have this information available)
 - on average
 - at its worst
 - at its best
 - right now

the average of these values as well as the pain "right now" will be recorded.

4.2.2 At the Treatment visit and the One Month Follow-Up Visit:

- On which side the painful sacroiliac sprain is located and whether it is anteriorly or posteriorly rotated.
- Distance in centimetres between the lowest and the highest PSIS: before and, for group 1 participants, after the corrective exercise.
- Pain score 0 (no pain) to 10 (worst imaginable pain) following the exercise, for group 1 participants.
- Impression of pelvic support belt for group 2 participants

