2.1 Randomization and group assignment

. After a potential participant has been examined, determined to be eligible and consents to participate they will be randomly assigned to treatment group 1, 2 or 3 according to the randomization scheme developed using “research randomizer”. Group 1 for immediately teaching the participant the SIFFT and appropriate exercises, group 2 for fitting of the pelvic support belt and group 3 for delayed treatment.

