3.2 Randomization and First Treatment Visit

- Prospective participants presenting with pain in their low back (below the waist) will be given a questionnaire about medications, alcohol and marijuana as well as the other therapies they currently use for pain relief. They will be given the BPI NRS pain severity questionnaire and ODI questionnaire .
- To rule out lumbar origin pain, physical examination will include straight leg raise, knee and ankle reflexes, Babinski, and tests for sensitivity to touch, pinprick and vibration below the knee. If these tests indicate lumbar origin pain, they will be eliminated from the study and replaced by another participant, but their number and data will be retained.
- Range of motion of the hips will then be tested and those with painful limitation of hip range of motion will also be eliminated and their data entered into the study.
- All participants will be tested for hypermobility using the Beighton score as, in the chart review, 15% of those with sacroiliac joint sprains were also hypermobile.

- The active straight leg raising test will be carried out to assess sacroiliac dysfunction^{xv}.
- Obvious leg length discrepancy (greater than 1½ cm) will be assessed as this causes scoliosis and sacroiliac strain as well as making it impossible to test the PSISs levels. The shorter leg will be prescribed a heel lift, participants will be sent for x-ray evaluation of leg length and excluded from the study.
- The lower back and buttocks will be examined for back mice or excess fat, making the exact location of the PSISs difficult to assess. If this is the case participants will be excluded but their data will be entered in the database.
- As gluteus medius and minimus as well as the piriformis muscle are major stabilizers, iliopsoas, biceps femoris and quadratus lumborum are secondary stabilizers of the sacroiliac joints, these may develop a compensatory overuse tendinosis in response to the sacroiliac malrotation, we will check for tenderness to palpation where these muscles insert on the ilium, the greater and lesser trochanter, the ischium, the head of the fibula and the edge of the sacrum.

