3.3 Assessment Visit (One Month after the Treatment Visit)

- Participants will answer the questionnaire about the medications, alcohol and marijuana as well as the other therapies they use for pain relief.
- They will be given the BPI NRS pain severity scales and the ODI questionnaire.
- They will once again be assessed, marked, measured and treated: this time participants in all treatment groups will be instructed on how to do the SIFFT and the corresponding corrective exercises. All of them will also receive the pelvic support belt.
- Those in group 1 will report on their use and effectiveness of the corrective exercises. They will then be fitted with a pelvic support belt.
- Those in group 2 will report on their use and the effectiveness of the pelvic support belt. They will then be taught the SIFFT and how to use the exercise corresponding to the direction of their sacroiliac malrotation.
- Those in group 3 will be instructed on how to do the SIFFT and the corresponding corrective exercises. They will also receive the pelvic support belt.
-

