Appendix 1: Brief Pain Inventory Pain Severity Scale

3.	Please rate your pain by circling the one number that best describes your pain at its worst in the last 24 hours.										
	0	1	2	3	4	5	6	7	8	9	10
	No										Pain as bad as
	Pain										you can imagine
4.	Please rate your pain by circling the one number that best describes your pain at its least in the last 24 hours.										
	0	1	2	3	4	5	6	7	8	9	10
	No										Pain as bad as
	Pain										you can imagine
5.	Please rate your pain by circling the one number that best describes your pain on the average .										
	0	1	2	3	4	5	6	7	8	9	10
	No										Pain as bad as
	Pain										you can imagine
6.	Please rate your pain by circling the one number that tells how much pain you have right now .										
	0	1	2	3	4	5	6	7	8	9	10
	No										Pain as bad as
	Pain										you can imagine

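### In the first study, the month 1 BPI is rated against a visible earlier score and the baseline BPI is not, so the secondary BPI change mixes two rating conditions

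*Combined protocol and SAP*

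**What the plan says.** The data list in section 4.2.1, headed as applying at all visits, records BPI "pain in the last 24 hours compared to previous recorded pain level (the participant will have this information available". The same list names the visits it covers: "Date of questionnaire (randomization and first treatment visit, one month assessment visit and two month reassessment visit". It cites Appendix 1 as the instrument.

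The Appendix 1 items are absolute ratings, for example "Please rate your pain by circling the one number that best describes your pain at its" worst or least. None of the four mentions an earlier score.

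The procedures sections describe giving the form and no more. Section 3.2 (first treatment visit) has "They will be given the BPI NRS pain severity questionnaire and ODI questionnaire"; section 3.3 (month 1) has "They will be given the BPI NRS pain severity scales and the ODI questionnaire". Section 4.1 also lists the BPI without the comparison clause. Before the first visit, section 3.1 mentions only a consent form and a suitability questionnaire.

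The BPI change is secondary in both sub-studies. For the first study, section 5.1.2A defines it as the "difference in the change in BPI NRS pain severity scores in the treatment visit questionnaire and at the assessment visit, one month later", each active group against control. For the follow-up study, section 5.2 plans a test of change within participants: "A student t-test will be done to assess the significance of the difference in BPI NRS pain severity score over a one month period".

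**The concern.** A change score is easiest to interpret when both of its ratings are made in the same way. Here the instruction cannot be followed at the first visit, because nothing has yet been recorded, and it can be followed from month 1 onward. The month 0 to month 1 change therefore combines the change in pain with whatever effect seeing the old number has on the new one.

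Participants also know what they received. Section 2.1 assigns group 1 to the exercise, with "group 2 for fitting of the pelvic support belt and group 3 for delayed treatment". Someone who knows they were treated may use the old number differently from someone who knows they are still waiting. At stake are the two secondary hypotheses of the first study, which both concern BPI change at month 1.

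**Working it through.** **Step 1: rating conditions at each visit.** The visits come from sections 3.2, 3.3 and 4.2.1; the outcomes come from section 5.1.

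| Visit | Earlier study BPI exists? | Condition under 4.2.1 |
|---|---|---|
| Month 0 | No | No reference score |
| Month 1 | Yes (month 0) | Reference score available |
| Month 2 | Yes (month 1) | Reference score available |

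The first-study change (0 to 1) crosses the two conditions. The follow-up change (1 to 2) does not.

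**Step 2: what cancels.** Write R0, R1 and R2 for the ratings that would be given with no score shown.

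- *Constant shift a, all arms, month 0 to 1.* Each arm's mean change becomes (R1 + a) − R0. In the active-minus-control difference, a − a = 0. Change within a single arm is still off by a.
- *Constant shift a, month 1 to 2.* (R2 + a) − (R1 + a) = R2 − R1, so the net effect is 0. Only an effect that depends on the score shown, or that differs between the two visits, would remain. No size is claimed for it.

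**Step 3: common pull toward the old score, month 0 to 1.** If a fraction k of the change is lost in every arm, the reported change is (1 − k)(R1 − R0), and the between-arm difference and the SD of change both shrink by (1 − k). The documents give no BPI effect, SD or k. The values here are assumptions: true difference 1.5 points, SD of change 2. With 20 per arm (section 2.2) and two-sided .05 (section 5.2), the standard error is 2 × √(2/20) = 0.632, the noncentrality is 1.5/0.632 = 2.37, and power on 38 degrees of freedom is 0.637.

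| k | Difference | SD | Power |
|---|---|---|---|
| 0 | 1.50 | 2.00 | 0.637 |
| 0.10 | 1.35 | 1.80 | 0.637 |
| 0.20 | 1.20 | 1.60 | 0.637 |
| 1/3 | 1.00 | 1.33 | 0.637 |
| 0.50 | 0.75 | 1.00 | 0.637 |

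Power is unchanged because difference/SD is unchanged. The same holds at SD 1.5 (0.869) and SD 2.5 (0.456). Under this model the harm is an understated effect, not lost power.

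**Step 4: a shift that differs by arm (generic illustration).** Suppose there is no true difference and reporting in the active arm is shifted by d points relative to control, in favour of treatment. The chance of a significant benefit is the upper-tail probability of a noncentral t with 38 degrees of freedom and noncentrality d/(SD × √(2/20)).

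| SD of change | d = 0 | d = 0.25 | d = 0.5 |
|---|---|---|---|
| 1.5 | 0.025 | 0.074 | 0.176 |
| 2.0 | 0.025 | 0.058 | 0.117 |
| 2.5 | 0.025 | 0.049 | 0.090 |

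These rates apply to an arm-differential shift from any cause. They do not estimate what the clause adds. If the clause added only 0.05 or 0.1 point (also assumed), the rate at SD 2 would be about 3.0% or 3.5%.

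The t-test on change is a stand-in: section 5.2 names chi-square tests and an analysis with covariates for the between-group comparison.

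**The case against.** **The clause is a deliberate choice.** The parenthesis shows that availability was intended, the form still yields absolute 0-10 ratings, and showing earlier scores may reduce within-person noise. The silence of sections 3.2, 3.3 and 4.1 is not a contradiction, since 4.2.1 can supply the detail. This is fair, and the point is therefore a design weakness rather than an inconsistency. But the protocol gives no rationale, and the choice cannot be applied at baseline.

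**Randomisation protects most of the contrast, and participants know their group anyway.** This stands. A common constant shift cancels, and self-reported pain is open to expectation bias without the display. Only the increment from the display can be laid at the clause's door, and nothing in the documents sizes it.

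**It is a secondary outcome in a pilot of 20 per group.** This stands and limits the priority.

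Three stronger readings are tempting and are not supported:

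- A reader might infer that BPI change is compromised in both sub-studies. At months 1 to 2 an earlier score is available at both ratings, so the conditions match.
- A reader might infer that the 5% to 18% false-benefit rates measure the damage done by the clause. They describe any differential shift of the assumed size.
- A reader might infer that the display itself differs by arm, because section 4.2.2 records a post-exercise pain score for group 1 only. The earlier level is not defined, so this is not strictly excluded. But the clause sits inside the BPI item, above the four BPI ratings, and the previous BPI is the natural reading.

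**Conclusion.** The point holds for the first study's secondary BPI outcomes. Baseline is rated without a reference score and month 1 with one, by participants who know their group. What can remain in the randomised contrast is an understated difference, if ratings are pulled toward the old score, and an added bias of unknown size and direction, if groups respond to the display differently. All magnitudes above rest on assumed shifts, pulls, effects and SDs.

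The clause is attached to the BPI and not to the ODI, so a reader should not extend the point to the primary outcome. It is a cheap improvement to a secondary outcome.

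**What to change.** In section 4.2.1, delete the part of the BPI item that asks for comparison with the earlier level, together with its parenthesis. State that the Appendix 1 form is given as printed at every visit and that no earlier pain score is shown.

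The documents do not say whether enrolment has begun. If some follow-up ratings were already taken with the score shown, flag them in the database and report the BPI comparison with and without them as a sensitivity analysis.

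The cost is one deleted phrase, withholding the earlier form at follow-up, and possibly slightly more within-person noise. A change partway through also leaves two rating procedures among the follow-up data, which is why the flag needs a stated use. The change makes the rating conditions the same at every visit; it does not remove bias from participants knowing their group.
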